#### **3.2. Sample size**

This non-inferiority trial aims to compare the caries preventive effect of applications of 38% SDF solution and that of combined 10% povidone iodine solution and 5% NaF varnish. A non-inferiority margin of 0.8 surface for the difference in the mean number of new caries surfaces over the 24-month study period is considered not clinically significant. The estimated sample size is based on the lower limit of the 2-sided 95% confidence interval for the difference set above the non-inferiority margin and the statistical power of the study being set at 90% ( $\beta=0.10$ ). The estimated standard deviation is 2.0, based on the results of a previous clinical trial conducted in Hong Kong (Tan et al., 2010). Using the statistical power analyses software, G\*Power (version 3.1.7; Franz Faul, Universität Kiel, Kiel, Germany), the total required number of elders in each group is calculated to be 133. Allowing for a drop-out rate of 20% in this 24-month study, an initial sample size of 166 subjects in each group or a total of 332 subjects is needed.

With a total sample size of 332 subjects and an estimated mean number of one untreated early/shallow root caries lesions per subject (Department of Health, 2013), there will be 332 root caries lesions in total or 166 lesions in each study group for caries arrest treatment. With this sample size, there is approximately 85% power that an absolute 15% difference in dental caries arrest rates between two groups can be shown to be statistically significant at the 5% level using Chi-square test when the overall success rate of the caries arrest treatment is around 80%.

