### **3.3. The baseline and follow-up examinations**

The baseline and follow-up examinations after 12 and 24 months will be carried out in the residential home by a single trained examiner. A portable dental chair, an intra-oral LED light, disposable dental mirrors and CPI probes will be used in the examination.

For each tooth that is not indicated for extraction, status of its crown and its root will be assessed and recorded separately. Caries diagnosis is based on visual and tactile inspection. No radiograph will be taken. Plaque and food debris that obscures visual inspection of the tooth surfaces will be removed. Four surfaces (mesial distal, buccal and lingual) per tooth will be examined and the status will be recorded using the following codes which basically follow the criteria recommended by the International Caries Detection and Assessment System (ICDAS II) Coordinating Committee (2009).

The oral hygiene status of the subject will be assessed and recorded by using the Visible Plaque Index (Ainamo & Bay, 1975). The presence or absence of visible plaque will be recorded on four surfaces (mesial, distal, buccal and lingual) per tooth.

The gingival status of the subject will be assessed and recorded using by the Gingival Bleeding Index (Ainamo & Bay, 1975). The presence or absence of bleeding within 10 seconds after running a probe across the gingival margin will be recorded on four surfaces (mesial, distal, buccal and lingual) per tooth.

Other information that will be recorded included whether the subject normally wears a removable partial denture or not, and the subject's general health status and medications that affect saliva flow rate.

The same examiner will carry out all the baseline and follow-up examinations without knowing the study group assignment of the subjects. It has been shown that good intra-examiner reproducibility can be achieved after training (Tan et al., 2010) and a random sample of 10% of the subjects will be re-examined during each examination to monitor intra-examiner reproducibility.

At the examinations, the subjects will be asked to report on their oral hygiene practices, use of fluoridated toothpaste and other topical fluoride agents, and use of dental services during the study period.

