### **3.4. Interventions**

Oral health education talk and instructions on how to keep good oral hygiene will be provided at baseline and every year to all the elders in the selected residential homes. Standard fluoride toothpaste with 1000-1500 ppm fluoride will be provided free to all the elders in the selected residential homes over the 24-month study period.

After the baseline examination, subjects satisfying the inclusion criteria of the study will be stratified into two groups according to the number of natural teeth in their mouth, those with 12 or fewer teeth and those with 13 or more teeth. The subjects will then be assigned to one of the two study groups by a research assistant using a block randomization method with a block size of 6. The stratified randomization procedure will help to ensure that

the numbers of teeth involved in the two study groups are balanced. The group assignment of the study subjects will be concealed and placed in a sealed envelope, and will not be made known to the examiner who evaluate the study outcomes.

The interventions for the two study groups will be provided by other dentists and are described below:

Group 1 – plaque on the root surfaces of all teeth in the subject’s mouth will be removed by a small brush and a 38% SDF solution (Saforide, Toyo Chemical, Japan ) will be applied onto the root surfaces using a microbrush/applicator. This will be repeated every year.

Group 2 – plaque on the root surfaces of all teeth in the subject’s mouth will be removed by a small brush and a 10% povidone iodine solution (Betadine, Mundipharma, Switzerland) will be applied, then followed by application of a 5% sodium fluoride varnish (Duraflor, Medicom, Canada) using a microbrush/applicator. This will be repeated every 4 months.

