### **3.5. Statistical analysis**

The collected data will be entered into a computer and analyzed using the software SPSS for Windows version 20. T-test and Chi-square test will be used, as appropriate, to assess the differences in the distribution of age, gender, denture wearing, number of remaining teeth, number of active caries lesions, oral hygiene practice and status, and gingival status at baseline between the two study groups.

The number of root surfaces with new caries found at each follow-up examination will be calculated. Two-sample t-test test will be used to find out if there are statistically significant differences between the two study groups in the number of tooth surfaces that have developed new dental caries. Both intention-to-treat and per protocol analysis will be performed to compare the effectiveness and efficacy of the two study preventive methods.

Two-level, tooth surface and subject, survival analysis will be used to assess the rates of arrest of active root surface caries in the two study groups (Wong et al. 2005). The statistical significance level for all tests will be set at 5%.

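### Randomisation is stratified by number of teeth but new root caries is compared by an unadjusted t-test, so the interval set against the 0.8-surface margin is slightly wider than it need be

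*Protocol*

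**What the plan says.** Three parts of the protocol bear on this.

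- **Design (section 3.4).** After the baseline examination subjects are "stratified into two groups according to the number of natural teeth in their mouth, those with 12 or fewer teeth" against those with 13 or more, then allocated in blocks of 6. The stated purpose is to balance tooth numbers between the groups.
- **Decision rule (section 3.2).** The margin is given as "A non-inferiority margin of 0.8 surface for the difference in the mean number of new caries surfaces over the 24-month study period", and the sample size is "based on the lower limit of the 2-sided 95% confidence interval for the difference set above the non-inferiority margin".
- **Analysis (section 3.5).** For new root caries: "Two-sample t-test test will be used to find out if there are statistically significant differences between the two study groups". No stratum term or covariate is given for this outcome. The only model in the section is the two-level survival analysis of caries arrest, which is the secondary outcome.

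Section 3.3 adds that for each tooth "status of its crown and its root will be assessed and recorded separately", so baseline root caries is also available for every subject.

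**The concern.** When randomisation is blocked within strata, the treatment difference is nearly free of variation between strata. The pooled standard deviation of a two-sample t-test still includes that variation. If the stratifying factor predicts the outcome, the t-test therefore overstates the uncertainty of its own estimate.

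Tooth number plausibly does predict this outcome. The endpoint is a count of root surfaces, four surfaces are examined per tooth, and eligibility starts at 6 teeth, so the number of surfaces at risk can differ several-fold between subjects. Non-inferiority is decided by where a confidence limit falls, so avoidable width makes the margin harder to meet.

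**Working it through.** **Inputs from section 3.2.** Margin 0.8 surface; SD 2.0; 2-sided 95% interval; power 90%; 133 evaluable per group. The true difference is taken as 0.

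**The plan's own figure.** The normal approximation gives n = 2 × (1.960 + 1.282)² × 2.0² / 0.8² = 131.3, so 132 per group. The noncentral t gives power 0.8993 at 132 and 0.9015 at 133. The stated 133 is therefore reproduced, and it is the right number for an unadjusted t-test.

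**Unadjusted interval at 133 per group.**
- SE = 2.0 × √(2/133) = 0.2453
- Half-width = 1.96 × 0.2453 = 0.481
- Power = Φ(0.8/0.2453 − 1.96) = Φ(1.302) = 90.4%

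**Effect of adjustment.** If the covariates explain a share R² of the outcome variance, the SE and half-width are multiplied by √(1 − R²). The protocol gives neither R² nor a mean increment, so both are assumptions here.

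**One way to size R².** Assume whole numbers of teeth uniform from 6 to 28, expected increment proportional to teeth, and total SD 2.0.
- Teeth: mean 17, variance (23² − 1)/12 = 44.
- Stratum means: 9 (7 of 23 values) and 20.5 (16 of 23 values).
- Between-stratum variance: (7/23)(16/23)(11.5)² = 28.0.
- For mean increment m, stratum R² = m² × (28.0/17²)/2.0², and tooth-count R² = m² × (44/17²)/2.0².

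| Mean increment | Stratum R² | Half-width | Power by formula | Tooth-count R² |
|---|---|---|---|---|
| no adjustment | – | 0.481 | 90.4% | – |
| 1.0 | 0.024 | 0.475 | 91.0% | 0.038 |
| 1.5 | 0.054 | 0.467 | 91.8% | 0.086 |
| 2.0 | 0.097 | 0.457 | 93.0% | 0.152 |

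**Why the formula overstates the gain.** Under stratified blocks the t-test's estimate already has the smaller variance; only its reported SE is too large. Write SE_u = 0.2453 for the reported SE and SE_a = SE_u × √(1 − R²) for the true one.
- The t-test's actual power is Φ((0.8 − 1.96 × SE_u)/SE_a). At R² = 0.097, SE_a = 0.2331 and this is Φ(1.370) = 91.5%, against 93.0% adjusted.
- Its one-sided error at the margin is Φ(−1.96 × SE_u/SE_a) = Φ(−2.06) = 2.0%, below the nominal 2.5%.

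**Simulation.** 15,000 trials per case, 266 subjects, blocks of 6 within stratum, negative-binomial increments, HC3 standard errors for the adjusted models:

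| Mean increment | Power: t-test | Power: + stratum | Power: + tooth count | One-sided error: t-test | One-sided error: + stratum | One-sided error: + tooth count |
|---|---|---|---|---|---|---|
| 1.0 | 89.8% | 90.0% | 90.2% | 2.2% | 2.4% | 2.3% |
| 1.5 | 90.1% | 90.9% | 91.7% | 2.3% | 2.6% | 2.5% |
| 2.0 | 90.7% | 92.1% | 93.7% | 2.1% | 2.5% | 2.5% |

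A separate simulation with normal outcomes gave the same pattern. At R² of 0.05, 0.10 and 0.20 the t-test's one-sided error was 2.1%, 1.7% and 1.7%, and the adjusted model's was 2.3% to 2.7%. At R² = 0.02 the two did not differ beyond simulation error.

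**A weaker relation.** If the increment rises with the square root of tooth count instead, stratum R² is only 0.007, 0.017 and 0.030. The half-width is then 0.479, 0.477 and 0.473, and power by formula is 90.6%, 90.8% and 91.2%.

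**A stronger one.** If tooth number and baseline root caries together explained 20% of the variance, the half-width would be 0.481 × √0.80 = 0.430 and power by formula about 95%. Nothing in the protocol supports or excludes that value, and baseline root caries was not simulated.

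**The case against.** The strongest reply is that nothing here is wrong. The t-test is valid, it matches the sample-size calculation, it meets the planned power, and under stratified blocks it errs only towards mild conservatism. All of that stands.

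The second reply is that the gain is small and rests on an assumed relation. That also stands. The simulated gain from the stratum alone is 0.2 to 1.4 points, and the lowest value is no larger than the Monte Carlo error of a single estimate (about 0.25 points). The square-root case shrinks the gain further, and the 20% case is purely illustrative.

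The third reply is that covariate adjustment is usually left to the SAP, which is not at hand. This carries less weight. The protocol is not silent: it names an unadjusted test that does not reflect its own randomisation.

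Finally, section 3.5 speaks of testing for a difference and mentions no interval; the interval comes from section 3.2. That is correct, and adding covariates does not by itself align the two sections. The analysis sentence should state the interval and the margin.

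**Conclusion.** The point holds as an efficiency improvement, not as an error. The stated analysis ignores the factor used to stratify randomisation, so the interval is somewhat wider than needed and the test slightly conservative. The planned size and power are unaffected.

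Under the proportional assumption with mean increments of 1.0 to 2.0, the stratum narrows the interval by about 1% to 5%. Simulated power rises by 0.2 to 1.4 points with the stratum and by 0.4 to 3.0 points with the exact tooth count. If tooth number predicts new caries only weakly, the gain is close to nil. The direction does not depend on these assumptions as long as tooth number has some predictive value; the size does.

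**What to change.** In section 3.5, make the primary analysis a linear model of new root-caries surfaces at 24 months on treatment, tooth number (the stratum, or preferably the count, which captures more variance) and baseline number of root surfaces with caries, with robust standard errors. Compare the adjusted mean difference and its 2-sided 95% confidence interval with the 0.8-surface margin. The coefficient is still a difference in mean surfaces, so the margin applies unchanged. Keep the unadjusted difference as a sensitivity analysis, and fix the model before unblinding.

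With 20% dropout allowed for, the balance achieved at randomisation may not fully persist among those analysed. The model also takes account of any such imbalance in tooth number.

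The cost is one or two sentences. Tooth number is needed to randomise and root status is recorded at baseline, so no new data, visits or subjects are required and the sample size stays as it is.
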